6.7. Efficacy

6.7.1. Clinically Symptomatic Respiratory Illnesses

Respiratory illness symptoms will be captured in an eDiary that subjects will complete daily (in the evening) at home after the Baseline visit. The eDiary will ask the subject to record whether a predefined set of respiratory illness symptoms have occurred during the past 24 hours that are new or reflect a change from normal baseline symptoms. The predefined symptoms include both respiratory symptoms (runny nose, sneezing, stuffy nose, sore throat, hoarseness, or cough) and general symptoms (headache, feverishness/chills, loss of appetite, body aches, or lack of energy).

A clinically symptomatic respiratory illness will be defined programmatically as the occurrence of 2 respiratory symptoms (runny nose/sneezing (programmatically considered one symptom), stuffy nose, sore throat, hoarseness, or cough) or 1 respiratory and 1 of the following general symptoms (headache, feverishness/chills or loss of appetite), with at least 1 unique respiratory symptom (runny nose, sneezing, stuffy nose, sore throat, hoarseness or cough) being reported on 2 or more consecutive entries in an eDiary, and at least 2 symptoms being at least moderate in severity. Subjects who have clinically symptomatic respiratory illness may include subjects with a common cold, bronchitis, influenza-like illness, or pneumonia.

Further details will be provided in the Statistical Analysis Plan (SAP).

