7.1. Adverse Events (AEs)

An AE is defined as any untoward medical occurrence (i.e., any unfavorable and unintended sign [including abnormal laboratory findings], symptom or disease) in a study subject from the Baseline Visit until the end of study visit (Week 20 Visit). Therefore, an AE may or may not be temporally or causally associated with the use of a medicinal (investigational) product. Pre-existing medical conditions/diseases are considered AEs if they worsen after the Baseline Visit.

In addition, all reports of intentional misuse and abuse of the study treatment are also considered an AE irrespective if a clinical event has occurred.

The occurrence of AEs must be sought by non-directive questioning of the subject at each visit during the study. AEs also may be detected when they are volunteered by the subject during or between visits or through physical examination finding, laboratory test finding, or other assessments.

Abnormal laboratory values or test results constitute AEs only if they fulfill at least one of the following criteria:

- they induce clinical signs or symptoms,
- they are considered clinically significant,
- they require therapy.

Clinically significant abnormal laboratory values or test results must be identified through a review of values outside of normal ranges/clinically notable ranges, significant changes from Baseline or the previous visit, or values which are non-typical in subjects with underlying disease. Investigators, along with other study staff, have the responsibility for managing the safety of individual subjects and identifying AEs.

All AEs (except RTI AEs) must be recorded on the AE eCRF accompanied by the following information:

- The severity grade using the U.S. Department of Health and Human Services, National Institutes of Health, National Cancer Institute's CTCAE v5.0, available at <https://evs.nci.nih.gov/ftp1/CTCAE/About.html>. For terms not included, the severity of the AE should be based on the following general guidelines:
 - Grade 1 Mild; asymptomatic or mild symptoms; clinical or diagnostic observations only; intervention not indicated.
 - Grade 2 Moderate; minimal, local, or noninvasive intervention indicated; limiting age-appropriate instrumental activities of daily living (ADL) (e.g., preparing meals, shopping for groceries or clothes, using the telephone, managing money, etc.).

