 - Grade 3 Severe or medically significant, but not immediately life-threatening; hospitalization or prolongation of hospitalization indicated; disabling; limiting self-care ADL (i.e., bathing, dressing and undressing, feeding self, using the toilet, taking medications, and not bedridden).
 - Grade 4 Life-threatening consequences; urgent intervention indicated.
 - Grade 5 Death related to AE.

NOTE:

- Any elevation of ALT, AST or total bilirubin > 3x ULN from the time of first dose of study drug should be reported as a Grade 3 (severe) AE.
- Its relationship to the study treatment:
 - Related
 - Not related
- Its duration (start and end dates)
 - If the event is ongoing, an outcome of either not recovered/ not resolved or recovering/ resolving must be reported.
- Whether it constitutes an SAE (see [Section 7.2](#) for definition of SAE) and which seriousness criteria have been met to define it as an SAE.
- Action taken regarding investigational treatment.

- Outcome (recovered/resolved, recovered/resolved with sequelae, not recovered/resolved, recovering/resolving, unknown, fatal).

Any beneficial therapeutic effects reported by subjects should also be recorded in the adverse events CRF.

All AEs (including diagnosed influenza) must be treated per local standard of care.

Treatment/action taken may include one or more of the following:

- No action taken (e.g. further observation only)
- Investigational treatment interrupted/withdrawn
- Concomitant medication or non-drug therapy given
- Hospitalization/prolonged hospitalization (see [Section 7.2](#) for definition of SAE)
- Study participation withdrawn

Once an AE is detected, it must be followed until its resolution or until it is judged to be permanent, and assessment should be made at each visit (or more frequently, if necessary) of any changes in severity, the suspected relationship to the investigational drug, the interventions required to treat it, and the outcome.

Any RTI that meets the definition of an SAE should be reported to resTORbio or designee as per [Section 7.2.2](#) and documented on the AE eCRF.

Any deterioration of asthma symptoms that requires treatment with systemic steroids should be recorded as an asthma exacerbation on the AE eCRF.

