7.2. Serious Adverse Event (SAE) Reporting

7.2.1. Definition of SAE

An SAE is defined as any AE (appearance of [or worsening of any pre-existing] undesirable sign(s), symptom(s) or medical condition(s)) which meets any one of the following criteria:

- Is fatal or life-threatening
- Results in persistent or significant disability/incapacity
- Constitutes a congenital anomaly/birth defect
- Requires inpatient hospitalization or prolongation of existing hospitalization, unless hospitalization is for:

- Elective or pre-planned treatment for a pre-existing condition that has not worsened since the start of study drug treatment.
- Treatment on an emergency outpatient basis for an event not fulfilling any of the definitions of a SAE given above and not resulting in hospital admission.
- Social reasons and respite care in the absence of any deterioration in the subject's general condition.
- Is medically significant, e.g. defined as an event that jeopardizes the subject or may require medical or surgical intervention.

All malignant neoplasms will be assessed as serious under “medically significant” if other seriousness criteria are not met.

Life-threatening in the context of a SAE refers to a reaction in which the subject was at risk of death at the time of the reaction; it does not refer to a reaction that hypothetically might have caused death if it were more severe (Annex IV, ICH-E2D Guideline).

Medical and scientific judgment should be exercised in deciding whether other situations should be considered serious reactions, such as important medical events that might not be immediately life threatening or result in death or hospitalization but might jeopardize the subject or might require intervention to prevent one of the other outcomes listed above. Examples of such events are intensive treatment in an ER or at home for allergic bronchospasm, blood dyscrasias or convulsions that do not result in hospitalization or development of dependency or abuse (Annex IV, ICH-E2D Guideline).

Any suspected transmission of an infectious agent via a medicinal product is also considered a serious adverse reaction.

All AEs (serious and non-serious) are captured on the CRF.

SAEs also require individual reporting to resTORbio or designee as per [Section 7.2.2](#).

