9.4.3.4. Adverse Events

All safety data will be displayed and analyzed using descriptive statistical methods. No formal inferential analysis is planned for safety comparison.

Frequency, intensity and causal relationship of AEs will be tabulated by system organ class after coding according to MedDRA. All AEs will be summarized by treatment group. The number and percentage of subjects who experienced at least 1 AE will be summarized by SOC and preferred term. The percentage will be based on the number of subjects in each treatment group. AEs will also be summarized by relationship to intervention and by severity within each treatment group. Deaths, SAEs, AEs leading to study drug discontinuation and AEs leading to study discontinuation will be tabulated and presented in data listings. Subject level data listings of all AEs will be presented. A subject with multiple AEs within a body system is only counted once towards the total of this body system.

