7.1. General Methods

All analyses and outputs will be produced using SAS® version 9.4 or later. Unless otherwise specified, efficacy and safety summaries will be presented for each treatment. All other summaries will be presented for each treatment and overall. Continuous variables will be summarized using the number of observations (n), mean, standard deviation (SD), median, minimum, and maximum. Categorical variables will be summarized using number of observations (n), frequency, and percentages of subjects.

All relevant subject data will be included in listings. All randomized subjects entered into the database will be included in subject data listings. All by visit summaries will use the nominal visit. Unscheduled visits will not be summarized but will be included in the listings.

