10.3. Adverse Events

An adverse event is any untoward medical occurrence associated with the use of a drug in humans, whether or not considered drug-related. All adverse events (AEs) will be coded using the MedDRA version 22.0 or higher. Only treatment-emergent adverse events, defined as any adverse events that start or increase in intensity on or after the first dose of double-blind treatment (Study Day 1), were collected in this study. The following listings of AEs will be provided by subjects:

- All AEs,
- Serious adverse events (SAEs)
- AEs leading to death
- AEs leading to study withdrawal
- AEs leading to study drug discontinuation
- Severe AEs
- Study drug related AEs
- Study drug related SAEs

Adverse Events will be included in summary tables by treatment received. An overall summary table of AEs through Week 20 will be produced for the following categories:

This document is confidential.

- Any AE
- Grade 1 (Mild) AEs, Grade 2 (Moderate) AEs, Grade 3 (Severe) AEs, Grade 4 (Severe and Life Threatening), and Grade 5 (Fatal) AEs
- Study drug-related AEs
- Serious AEs
- Study drug-related Serious AEs
- AEs leading to permanent study drug discontinuation
- AEs leading to study discontinuation
- AEs leading to death

All AEs will be classified by SOC and PT. Frequency count of AEs, the number of unique subjects experiencing an AE, percentage of unique subjects experiencing an AE and total number of events will be tabulated by treatment. For the number of unique subjects reporting, if a subject reported more than one AE that was coded to the same SOC or PT, the subject will be counted only once for that specific SOC or PT.

The following summaries of AEs will also be provided:

- AEs by SOC and PT
- Treatment-related AEs by SOC and PT
- AEs by SOC, PT and maximum severity
- AEs by SOC, PT and causality relationship
- Serious AEs by SOC and PT
- Serious treatment-related AEs by SOC and PT
- AEs leading to study withdrawal by SOC and PT
- TEAEs leading to study drug discontinuation by SOC and PT
- AEs leading to death by SOC and PT

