16.2.6.1.1	Respiratory Symptom Questionnaire	Full Analysis Set
16.2.6.1.2	Clinically Symptomatic Respiratory Illness	Full Analysis Set
16.2.6.2.1	Nasopharyngeal Swab for Pathogen PCR	Full Analysis Set
16.2.6.2.2	Mid-Turbinate Nasal Swab for Pathogen PCR	Full Analysis Set
16.2.6.2.3	Rapid Influenza Antigen Diagnostic Test (RIDT)	Full Analysis Set
16.2.6.2.4	Sputum Gram Stain and Culture	Full Analysis Set
16.2.6.3.1	Hospitalization	Full Analysis Set
16.2.6.3.2	Emergency Room Visit	Full Analysis Set
16.2.6.3.3	Urgent Care Facility Visit	Full Analysis Set
16.2.6.3.4	Skilled Nursing Facility Admission	Full Analysis Set
16.2.6.3.5	EQ-5D-5L Questionnaire	Full Analysis Set
16.2.6.3.6	Asthma Exacerbation	Full Analysis Set
16.2.6.3.7	Biomarkers	Full Analysis Set
16.2.7.1	Adverse Events	Safety Set
16.2.8.1.1	Hematology	Safety Set
16.2.8.1.2	Blood Chemistry	Safety Set
16.2.8.1.3	Urinalysis	Safety Set
16.2.8.2.1	Vital Signs	Safety Set
16.2.8.2.2	Electrocardiogram (ECG)	Safety Set
16.2.8.2.3	Physical Examination	Safety Set
16.2.8.2.4	Chest X-Ray	Safety Set
16.2.8.2.5	Vital Status	Safety Set

This document is confidential.

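### Does leaving non-serious respiratory infections off the adverse-event form undermine the AE tables or the primary imputation?

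*Protocol*

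**What the plan says.** Protocol 7.1 sets the recording rule: "All AEs (except RTI AEs) must be recorded on the AE eCRF accompanied by the following information". It then restores one group to the AE form: "Any RTI that meets the definition of an SAE should be reported". Protocol 7.2.1 says, more broadly, "All AEs (serious and non-serious) are captured on the CRF". Protocol 5.4.2 requires AEs that interrupt or stop study drug to be in the eCRF. Neither document names a form page for a non-serious RTI.

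On the analysis side, SAP 10.3 states "An overall summary table of AEs through Week 20 will be produced for the following categories", and the first category is any AE. Protocol 9.4.3.4 also summarises and lists all AEs, and adds that "AEs leading to study drug discontinuation and AEs leading to study discontinuation will be tabulated and presented in data listings". Neither section mentions an RTI exception.

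The primary imputation (Protocol 9.4; SAP 7.3 and 9.2.1) concerns subjects who left the study early without meeting the CSRI definition. They count as events if they left because of an RTI AE or RTI SAE, and as non-events if they left for any other reason.

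**The concern.** Respiratory infection is the illness the trial expects to see most. If RTIs that are not serious sit outside the AE form, a reader of the any-AE row and the infection rows cannot tell whether they are included. AE reporting is part of a declared secondary endpoint, so the choice seems to deserve a written rule.

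The CSRI analyses do not stand in for investigator-recorded infections. CSRI is computed from the eDiary ("A clinically symptomatic respiratory illness will be defined programmatically as the occurrence of 2 respiratory symptoms", or one respiratory plus one general symptom) and needs at least two symptoms of moderate or worse severity. A milder infection might then be counted nowhere.

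The imputation adds a second worry. Leaving because of an RTI is the only discontinuation reason that becomes an event, and it applies only to subjects without a CSRI, so the eDiary cannot settle it. If the AE form does not hold the infection, the derivation needs another source, and none is named.

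**Working it through.** **1. Do the recording rules conflict?** Protocol 7.1 speaks of the AE eCRF; 7.2.1 and 5.4.2 speak of the CRF or eCRF as a whole. Section 7.1 removes a requirement to use one form and does not forbid its use. The passages agree if non-serious RTIs are held on another page. There is an obvious occasion for recording them: the unscheduled respiratory illness visit has investigator evaluation and recording of treatments (Protocol 3.1), and AE assessment is marked for that visit in Table 6-1. Protocol 6.8 sends methods of recording safety assessments to the study operations manual, which is not public, so this does not prove that such a page exists.

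**2. Would a mild RTI be lost?** A nasopharyngeal swab is triggered by one respiratory symptom on two consecutive eDiary entries, with no severity threshold (Protocol 6.7.2 and Table 6-1, footnote 14). SAP 9.5.1 analyses every positive viral result by arm, whether or not a CSRI is present (Table 14.2.3.1). RTI-related hospitalisations and ER visits are analysed by arm in SAP 9.5.3 and 9.5.5. SAP 7.1 promises that "All relevant subject data will be included in listings", and the index in SAP 17 lists the symptom questionnaire, both kinds of swab, rapid influenza tests and sputum. What escapes a by-arm summary, if the AE tables leave RTIs out, is a mild infection with no virus detected and no hospital or ER visit.

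**3. Planned power.** Inputs from Protocol 9.6: 28.2% and 19.7%, 1066 subjects (533 per arm), two-sided 0.05, likelihood-ratio chi-square. Exact enumeration without covariates gives 90.4%, which reproduces the stated 90%.

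**4. Missed RTI discontinuations.** Treat a missed subject as an event scored as a non-event.

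| Missed, placebo / RTB101 (assumed) | Rates used | Power |
|---|---|---|
| 0 / 0 | 0.282, 0.197 | 90.4% |
| 3 / 2.1 | 0.282 − 3/533, 0.197 − 2.1/533 | 89.7% |
| 5 / 3.5 | 0.282 − 5/533, 0.197 − 3.5/533 | 89.2% |

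With no true effect (28.2% in both arms), missing 5 in each arm leaves the chance of a significant result favouring RTB101 at 2.5%.

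**5. The any-AE row.** Planned CSRI subjects: 0.282 × 533 = 150 placebo and 0.197 × 533 = 105 RTB101. Let o be the share of subjects with some other AE (same in both arms, independent of CSRI) and c the share of CSRI subjects recorded with a non-serious RTI AE. The documents give neither. With RTIs counted, the any-AE proportion is o + (1 − o) × c × p, so the added difference is (1 − o) × c × (28.2 − 19.7) points.

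| o | Any AE with RTIs, c = 1 (placebo / RTB101) | Added difference, c = 1 | Added difference, c = 0.5 |
|---|---|---|---|
| 30% | 49.7% / 43.8% | 0.7 × 8.5 = 5.95 | 2.98 |
| 50% | 64.1% / 59.9% | 0.5 × 8.5 = 4.25 | 2.13 |
| 70% | 78.5% / 75.9% | 0.3 × 8.5 = 2.55 | 1.28 |

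Every figure in the last two columns is the assumed efficacy difference of 8.5 points multiplied by a number below 1.

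**The case for a change.** The strongest case for acting is that the remedy is cheap and best done before unblinding. The any-AE row can move by several points depending on an unstated choice, and a choice made after unblinding invites suspicion. By-arm RTI counts also have safety value: Protocol 3.2 wants to show that no viral infection is enhanced, and Protocol 1.2.2 reports a nominal RTI increase in Phase 2b smokers. It is true that the inclusion choice is unstated and that a footnote would help the reader.

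The rest is weaker. If the drug prevents infections, leaving RTIs out of the AE tables does not flatter it. If it caused more of them, the first four hypotheses in SAP 9.1 and the viral analyses would show that. The number of points rests on assumed background rates, and the windows differ: the planning rates run to Week 16, the AE tables to Week 20.

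A second argument is that SAP 10.3 sets a missing severity to severe and a missing relationship to related, so RTIs brought in from another page could be misclassified. Nothing in the documents shows that such records would be merged into those tables.

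On imputation, a one-sided loss would matter more. By the normal approximation, starting from 150 and 105 events (power 89.9%), five missed placebo subjects and none on RTB101 give 82.5%. Nothing in a double-blind trial suggests that pattern, and such a loss would lower the placebo event rate, which works against the drug. Reasons for stopping treatment and for withdrawing consent are recorded (Protocol 5.5.2 and 5.5.3), and SAP 8.1 tabulates reasons for leaving the study.

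**Conclusion.** No change to the plan is called for. The documents leave unsaid where a non-serious RTI is recorded, which field shows that a subject left because of one, and whether the AE tables count it. These are details for form-completion guidance, dataset specifications and table footnotes, and competent analysts will settle them from data already collected.

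The primary analysis is insensitive to the gap: about 0.7 to 1.2 points of power if a few subjects are missed in proportion to planned rates, and no rise in false positives when losses are equal. That assumes such discontinuations are few; the documents give no count. The AE row could differ by about 1.3 to 6.0 points between arms under the assumed rates, but that is the efficacy effect seen again, and infections are reported by arm elsewhere. Only mild illness with no virus detected and no hospital or ER visit could lack a by-arm summary, and its daily symptoms are still listed.

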For AEs presented by relationship to study treatment, the strongest relationship to study treatment(s) during the clinical trial will be presented for each subject if coded to the same SOC or PT. For AEs presented by severity, the worst severity during the clinical trial will be presented for each subject if coded to the same SOC or PT. If either relationship or severity is missing, then the strongest relationship (related) or worst severity (severe) will be assigned.

This document is confidential.

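### Protocol 7.1 sends beneficial effects to the adverse-event CRF, and SAP 10.3 has no rule to keep them out of the AE summaries

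*Protocol*

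**What the plan says.** Protocol 7.1 opens with the definition: "An AE is defined as any untoward medical occurrence (i.e., any unfavorable and unintended sign [including abnormal laboratory findings], symptom or disease". It then lists what must accompany each AE on the eCRF: severity grade, relationship, dates, seriousness, action taken with study drug, and outcome. Directly after that list comes the instruction at issue: "Any beneficial therapeutic effects reported by subjects should also be recorded in the adverse events CRF".

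SAP 10.3 gives its own definition: "An adverse event is any untoward medical occurrence associated with the use of a drug in humans, whether or not considered drug-related". It says that only treatment-emergent events, meaning those starting or worsening "on or after the first dose of double-blind treatment (Study Day 1), were collected in this study". On tabulation it says "All AEs will be classified by SOC and PT", and it promises, by treatment, "Frequency count of AEs, the number of unique subjects experiencing an AE, percentage of unique subjects experiencing an AE and total number of events". For incomplete records the rule is: "If either relationship or severity is missing, then the strongest relationship (related) or worst severity (severe) will be assigned".

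Protocol 9.4.3.4 also summarises all AEs by treatment group, and states that the safety comparison is descriptive, with no formal inference.

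**The concern.** A benefit is not an unfavourable occurrence, so the instruction places on the AE form something that the form is not meant to hold. That would be harmless if a later step took it off again, but neither document describes one. Protocol 7.1 does make an exception where it wants one: respiratory tract infection AEs are excepted from the general recording rule. It makes no comparable provision for benefits.

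Safety and tolerability through Week 20 is a stated secondary objective. Because no safety test is planned, the counts and percentages are themselves the safety evidence. A benefit counted as an AE puts a non-harm into those figures, and the rule for blank items could also put it into the severe or drug-related rows.

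**Working it through.** No figure in the plan bears on this, so there is nothing to reproduce. The check follows a single benefit report through the documents.

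1. **Entry.** A subject tells the site of a beneficial effect. Protocol 7.1 has the site enter it on the AE CRF. By the definition in the same section it is not an AE. The two statements conflict.

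2. **Identification.** The items that Protocol 7.1 lists for an AE record include no marker for benefit, and the outcome categories (resolved, not resolved, fatal and so on) do not suit one. The list is not the CRF layout. The eCRF itself is not among the documents, so a separate field may exist; the documents do not show one.

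3. **Selection for analysis.** SAP 10.3 defines an AE as untoward, which excludes a benefit in principle. It then describes the collected events as treatment-emergent AEs, which overlooks the Protocol 7.1 instruction. It assigns no one to apply the definition record by record and states no exclusion. SAP section 12, on changes from the protocol, does not raise the matter.

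4. **Counting.** A record that is kept and coded adds one to the event count. It changes a subject count only if the subject is not already counted in that row. With about 533 subjects per arm, the most that one affected subject can add to the arm's any-AE percentage is 1/533 = 0.19 percentage points. A subject who has any other AE adds nothing to it. This is a ceiling per subject, not an estimate, because the number of such subjects is unknown.

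5. **Blank items.** Severity grading does not naturally apply to a benefit, so a blank grade is conceivable. If it is still blank at analysis, SAP 10.3 assigns the worst severity, and a blank relationship becomes related.

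6. **Reach.** The primary endpoint is derived from the eDiary (Protocol 6.7.1, SAP 7.2.1). In the fixed testing sequence, the one endpoint counted from AE reports is the urinary tract infection rate (H8), and a report of benefit would not plausibly be coded as such an infection. What remains exposed is the descriptive AE summaries.

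**The case against.** The strongest reply is that SAP 10.3 tabulates AEs, not forms. It opens with the untoward-occurrence definition, and a programmer or coder who applies it drops a benefit. There are other safeguards too. Protocol 8.2 provides automatic validation checks, and Protocol 8.3 has the CRO review CRF data for completeness and query the sites, so most blank severity or relationship fields should be filled before lock. A benefit must also pass through MedDRA coding. The by-subject listing in the protocol synopsis carries the verbatim term, so a stray entry would be visible.

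Most of this stands. It turns a certainty into a possibility and makes the missing-item route less likely. It does not close the gap, because a definition is not a filter. The general data checks look for incomplete or inconsistent records, and a fully completed benefit entry made as the protocol instructs need not trigger any of them.

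A reader might go further and infer that RTB101's AE rate would be inflated because a working drug produces more benefit reports. The documents do not support that. The instruction applies to both arms under blinding, and the intended benefit is that a respiratory illness does not occur, which subjects would seldom report as an effect. Any imbalance between arms is conjecture.

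**Conclusion.** The point holds as a small, definite inconsistency. Protocol 7.1 routes beneficial effects to the AE CRF against its own definition of an AE, and SAP 10.3 has no rule to identify or exclude them. In either arm they could enter the AE counts and, if items stay blank, be shown as severe or related.

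It is tempting to say that the SAP tabulates everything on the form, so that benefits will be counted. The SAP does not say so, and the correct word is could. Nor can a size or direction be given, since the documents contain no number or rate of such reports. The effect is probably small.

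The conclusion rests on two assumptions: that no CRF field or data-handling rule outside these two documents already separates benefit entries, and that sites follow the instruction as written. It concerns the descriptive safety tables only, and neither the primary analysis nor its error control is affected. Severity is minor.

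**What to change.** Either delete the sentence from Protocol 7.1 or direct benefit reports to a separate comment page. Protocol 11.1 requires a written amendment for any protocol change, so this is best carried with another amendment.

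If entries may already exist, search the AE verbatim terms for them and flag them before unblinding; the blind data review meeting in SAP 5.4 and section 6 is a natural place. Add to SAP 10.3 that flagged records are excluded from every AE summary and from the rule for missing severity and relationship, and that they remain in a by-subject listing so that the exclusion can be audited.

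The cost is one protocol sentence or one CRF flag, a sentence or two in the SAP, and one filter in the AE programs. No sample size, endpoint or test changes.
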